Urinalysis (all tests should be performed on random spot urine. If random spot testing is not possible then 24hr urine can be performed, but only if pre-agreed with sponsor in writing) Including: 
 • Protein:Creatinine Ratio (PCR)² • Albumin:Creatinine Ratio (ACR)³ • urinary creatinine • urinary phosphate • urinary glucose (Can be performed quantitatively or by dipstick; optional if pre-agreed with sponsor in writing) • beta-2 microglobulin (optional if pre-agreed with sponsor in writing) 	X	X	X	X	X	X	X	X	X	X	X	X
ECG	X											
CD4 & CD8 (count / % and ratio)	X	X	X						X	X		X
HBV/HCV (HBV antigen test (including HbsAG, anti-HBc and HBsAb) and HCV antibodies test (if test positive for HCV antibodies, test for HCV	X					X						

² Random spot protein value will also be requested. 24hr urinary protein should be performed if PCR is not available, if pre-agreed with sponsor in writing (optional if pre agreed with sponsor in writing)

³ Random spot albumin value will also be requested. 24hr urinary albumin should be performed if ACR is not available, if pre-agreed with sponsor in writing (optional if pre-agreed with sponsor in writing)

CONFIDENTIAL

	SCREENING	BASELINE (within 28 days of screening)	WEEK 4 (+/- 7 days)	WEEK 12 (+/- 7 days)	WEEK 24 (+/- 7 days)	WEEK 48 (+/- 7 days)	WEEK 52 (+/- 7 days)	WEEK 60 ¹ (+/- 7 Days)	WEEK 72 (+/- 7 days)	WEEK 96 (+/- 7 days)	30 Day FU (+/- 7 days) (by phone)	Early termination visit
Both treatment arms to complete all visits.												
RNA, if positive and chronic for either HBV or HCV, add AST test to the biochemistry panel at screening visit. Also include Hep B surface antibodies post vax levels)												
Haematology Including: 
 • Platelet count • RBC Count (indices MCV & MCH) • WBC count (absolute) • Haemoglobin • Hamatocrit RBC Count indices: 
 • MCV • MCH Automated WBC differentials: 
 • Neutrophils • Lymphocytes • Monocytes • Eosinophils • Basophils 	X	X	X	X	X	X	X	X	X	X	X	
Clinical chemistry (Fasted for at least 10 hours except for screening) Including: 
 • Urea • Chloride • Alkaline phosphatase • Creatine phosphokinase • Creatinine • Calcium • Phosphate • Glucose (optional in urine if agreed with sponsor in writing) • Total bilirubin • Potassium 	X*	X*	X	X	X*	X*	X	X	X	X*		X

CONFIDENTIAL

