(h) Changes from baseline in laboratory parameters at week 24, 48 and 96.

The evolution of haematology parameters (including haemoglobin, white cell count and differential, platelets) and biochemistry parameters (including sodium, glucose, ALT, AST, and total bilirubin) according to the treatment group will be described by boxplots for each treatment group at baseline, week 24, 48 and 96. The changes from baseline will be compared between the two treatment groups

using mixed models for repeated measures with random intercept and unstructured covariance matrix adjusted for baseline value. The model will include treatment group, time and interaction between treatment group and time, and baseline value. Time will be considered as categorical variables. Data will be also summarised in tables by mean and standard error.

If the residual of the mixed model is not normally distributed and therefore does not allow the use of parametric test, the non-parametric Mann-Whitney-Wilcoxon test will be used to compare the changes from baseline to week 24, 48 and 96 between the two treatment groups.

(i) Changes from baseline in renal markers, bone markers, and fasting lipids at week 24, 48 and 96.

The evolution of renal markers (including blood creatinine, blood creatinine clearance (eGFR), urine creatinine, urine protein, urine protein/creatinine ratio, blood albumin, urine albumin, urine albumin/creatinine ratio, urine beta 2 microglobulin, urine creatinine clearance (eGFR), potassium, blood phosphate, urine phosphate), bone markers (including ALP) and lipids fasting parameters (including total cholesterol, HDL, LDL, triglycerides) according to the treatment group will be described by boxplots for each treatment group at baseline, week 24, 48 and 96.

The changes from baseline will be compared between the two treatment groups using mixed models for repeated measures with random intercept and unstructured covariance matrix adjusted for baseline value. The model will include treatment group, time and interaction between treatment group and time, and baseline value. Time will be considered as categorical variables. Data will be also summarised in tables by mean and standard error.

If the residual of the mixed model is not normally distributed and therefore does not allow the use of parametric test, the non-parametric Mann-Whitney-Wilcoxon test will be used to compare the changes from baseline to week 24, 48 and 96 between the two treatment groups.

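### SAP 9(i) compares urine beta-2 microglobulin and urine phosphate between arms as spot-urine concentrations with no dilution correction, although urine creatinine is in the same panel

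*SAP*

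**What the plan says.** Change in renal markers at weeks 24, 48 and 96 is a named secondary safety endpoint (SAP section 3.2.2, item (i)).

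- **Sample.** The urinalysis row of Protocol Appendix 1 states that "all tests should be performed on random spot urine". The exception reads: "If random spot testing is not possible then 24hr urine can be performed, but only if pre-agreed with sponsor in writing". Urinary creatinine is in the same row. The entry for one of the two markers is "beta-2 microglobulin (optional if pre-agreed with sponsor in writing".
- **Markers.** SAP section 9(i) names "urine creatinine, urine protein, urine protein/creatinine ratio, blood albumin, urine albumin, urine albumin/creatinine ratio", and its list continues with "urine albumin/creatinine ratio, urine beta 2 microglobulin, urine creatinine clearance (eGFR), potassium, blood phosphate, urine phosphate". Protein and albumin therefore appear both raw and as a creatinine ratio. Beta-2 microglobulin and phosphate appear without a ratio.
- **Model.** "The model will include treatment group, time and interaction between treatment group and time, and baseline value". If residuals are not normal, "the non-parametric Mann-Whitney-Wilcoxon test will be used to compare the changes from baseline to week 24, 48 and 96".
- **Derived variables.** SAP section 3.3 defines change and percent change from baseline. It defines no ratio for either marker, and it specifies a log transformation only for HIV DNA.

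**The concern.** The concentration of a substance in a spot sample reflects both how much is excreted and how much water it is excreted in. If dilution differs between a participant's visits, that difference enters both the baseline and the follow-up value, and so the change. Neither change nor percent change removes it, a rank test on the changes does not, and the model has no urine-creatinine term.

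The plan already uses the remedy elsewhere. SAP 9(i) has ratios for protein and albumin, and Protocol sections 6.15 and 6.16 rely on a urine albumin/creatinine ratio. Only these two markers are left uncorrected, and they are the urinary entries in 9(i) most directed at the tubule. With about 50 controls, avoidable noise in a safety comparison pushes the result towards finding no difference.

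**Working it through.** The documents give no SD, effect size or power for any urine marker, so there is no figure of the plan's own to reproduce on this point. What follows shows direction and an assumed range.

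**Inputs.** From the documents: 100 and 50 participants (SAP section 5), and two-sided 0.05 (stated in SAP section 8.2 for secondary efficacy, assumed here for 9(i)). The expected 15% loss to follow-up is not applied. Assumed: all SDs.

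**Step 1, model.** On the log scale, log(concentration) = log(marker per unit creatinine) + log(urine concentration factor), with the two parts independent. Write s_m for the marker SD, s_h for the dilution SD and k = s_h/s_m. If the ratio removes dilution completely, then:

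- efficiency of the raw concentration relative to the ratio = s_m²/(s_m² + s_h²) = 1/(1 + k²)
- widening of the confidence interval = √(1 + k²)

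**Step 2, power.** Choose the difference that gives the ratio 80% power: (1.960 + 0.842) × √(1/100 + 1/50) = 0.485 SD. Power for the raw concentration is then Φ(2.802/√(1 + k²) − 1.960). At k = 1 this is Φ(1.981 − 1.960) = 51%.

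| k | Efficiency | Information lost | Interval width | Power (80% with ratio) | Effective N of 150 |
|---|---|---|---|---|---|
| 0.25 | 0.94 | 6% | ×1.03 | 78% | 141 |
| 0.5 | 0.80 | 20% | ×1.12 | 71% | 120 |
| 0.75 | 0.64 | 36% | ×1.25 | 61% | 96 |
| 1 | 0.50 | 50% | ×1.41 | 51% | 75 |
| 1.5 | 0.31 | 69% | ×1.80 | 34% | 46 |

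**Step 3, if creatinine adds its own noise.** With visit-to-visit log SD s_c in creatinine, the efficiency becomes (s_m² + s_c²)/(s_m² + s_h²). Taking s_c = 0.3 as an assumption:

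- s_m = 0.4, s_h = 0.4: 0.25/0.32 = 0.78, so the loss is 22% instead of 50%
- s_m = 0.4, s_h = 0.7: 0.25/0.65 = 0.38, so the loss is 62% instead of 75%
- s_m = 0.6, s_h = 0.4: 0.45/0.52 = 0.87, so the loss is 13% instead of 31%

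The ratio is better as long as s_c is below s_h; at s_c = s_h the two are equal.

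**Step 4, the kind of analysis planned.** Steps 1 to 3 are on the log scale, and SAP 9(i) specifies no log. A simulation at 100/50 therefore compared baseline-adjusted analyses on both scales, and the Mann-Whitney test on change. It assumed a between-person log SD of 0.5 for the marker and 0.3 for dilution, visit-level log SDs of 0.3 to 0.7 for each, and creatinine noise of 0.1 to 0.2. The true effect was set for about 80% power with the log ratio.

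| Analysis | Power, ratio | Power, concentration |
|---|---|---|
| Log scale, baseline-adjusted | 78–80% | 23–71% |
| Untransformed, baseline-adjusted | 58–67% | 13–47% |
| Mann-Whitney on change | 60–70% | 15–52% |

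The concentration lost power in every scenario, and the rank-test fallback did not recover it. In all of these scenarios creatinine noise was smaller than dilution noise.

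**The case against.** The strongest reply is that the size is unknown. No SD is given; at k = 0.25 the loss is 6%, and the simple formula favours the ratio by treating creatinine as noise-free. That stands. A reader might infer that these markers lose most of their precision. Under the simple model the loss passes about one third only from k of about 0.75, and the documents do not say where k lies.

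Several narrower replies also stand:

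- The marker list in SAP 9(i) is introduced as non-exhaustive, and Protocol section 6.18 leaves urine to local laboratories without stating reporting units. A ratio is therefore unspecified, not ruled out. It is still not prespecified.
- Beta-2 microglobulin is optional by agreement, so it may be missing at some sites whatever the analysis.
- A reader might infer that a real tubular problem would go unseen. The definition of proximal renal tubule dysfunction in Protocol section 6.15 uses serum creatinine, serum phosphate, glycosuria, potassium and bicarbonate. It uses neither of these two urine markers, so monitoring of individual participants is unaffected.
- A reader might infer that raw spot and 24-hour values will be pooled. Appendix 1 permits timed collection by agreement, but neither document says how such results are recorded or combined.
- A reader might want raw urine protein, albumin and creatinine removed. Protein and albumin stand beside their ratios, and the Appendix 1 footnotes request the spot values deliberately. No loss of precision follows from reporting them.

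None of this answers the central point. As written, two markers enter the between-arm comparison uncorrected while the means to correct them is in the same panel.

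**Conclusion.** The point holds for two markers, urine beta-2 microglobulin (where collected) and urine phosphate. That the correction is missing follows from the text. That this costs precision follows if dilution varies between visits by more than creatinine excretion does. The amount rests on assumed SDs: from about 6% of the information at k = 0.25, through 50% at k = 1, to 69% at k = 1.5, and less with noisy creatinine. The documents do not support a claim of bias, because dilution should fall equally on the randomised arms. This is a modest improvement to a secondary safety analysis in a self-described pilot. It is worth making because it uses data already planned and costs almost nothing.

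**What to change.** In SAP 9(i), replace the raw urine beta-2 microglobulin and urine phosphate entries with the beta-2 microglobulin/creatinine and phosphate/creatinine ratios from the same sample, analysed on the log scale. Add both to the derived variables in SAP section 3.3. Keep the protein/creatinine and albumin/creatinine ratios as the compared outcomes for those two markers. Raw urine creatinine, protein and albumin may stay as descriptive summaries.

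A urine ratio is preferable to a fractional excretion. The latter needs serum creatinine, which Protocol Table 1.0 says dolutegravir can raise through blocked secretion without a significant effect on GFR, so it could differ between arms for that reason alone.

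The cost is SAP wording, one division per sample and a slight dependence of the ratio on muscle mass. No new data are needed.

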2.2 Secondary objectives

- To investigate whether switching patients to DTG/RPV FDC is associated with improvement of lipid profile, patient satisfaction, quality of life and potential for drug-drug interactions, investigated over time through 96 weeks with evaluation (and comparison to control arm) at week 24, 48 and 96.
- To evaluate DTG & RPV trough concentrations
- Changes in cell associated virus (using Peripheral Blood Monoclonal Cell (PBMC) analysis)

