6.8 Study on treatment visits

Study Visits: weeks 4, 12, 24, 48, 52, 72 and 96 (all visits +/- 7 days visit window). An optional visit at week 60 may be performed for subjects on the control arm (3 months after therapeutic modification) as required per national guidelines. The following evaluations and procedures are to be performed pre dose:

- Symptoms review and adverse events
- Review of concomitant medications
- Physical examination (symptom directed)

CONFIDENTIAL

- Weight
- Vital signs (pulse, blood pressure: after 10 minutes resting)
- Viral load
- Alcohol intake, smoking habit and recreational drug use (week 24, 48 and 96)
- Adherence assessment (including date/time of last dose on PK days including ETV visit and/or in the event of virological failure)
- Urinalysis (see Appendix 1) (week 24, 48 and 96)
- Week 48 (and screening) only: HBV antigen test (including HbsAG, anti-HBc and HBsAb, if done as per standard practice) and HCV antibodies test (if test positive for HCV antibodies, test for HCV RNA, if positive and chronic for either HBV or HCV, add AST test to the biochemistry panel at screening visit. Hep B surface antibodies post vaccination levels to be included in assessment, if this is done as per local practice)
- Laboratory evaluations: haematology and biochemistry (fasting)
- Total cholesterol and lipids (HDL, LDL and triglycerides) (fasted)
- PBMC (BL & week 48, 96 & ETV only)
(Required unless exemption documented in site contract i.e. if site does not have capacity to process)
- Pre-dose blood sampling for measurement of DTG & RPV (PK assessment) (week 4 & 48 (experimental arm), week 52 (deferred switch patients) and week 96 (both arms)). Plus pre- or post-dose (as appropriate) at early termination visit and/or in the event of virological failure (see section 6.12). A post dose sample will be taken within 20-28 hours
- HIV RNA viral load
Note. In event of viral load failure follow section 6.18 viral failure & resistance assessment procedures.
- CD4 & CD8 count / % (week 24, 48, 72 and 96)
- EuroQoL questionnaire (week 24, 48 and 96)
- Pittsburgh sleep questionnaire (week 24, 48 and 96)
- Patient treatment satisfaction questionnaire (week 24, 48 and 96)
- DDI assessment (week 24, 48 and 96)
- Adherence assessment
- Drug Dispensing (not at week 96)

CONFIDENTIAL

- Pregnancy test for WOCBP (β -HCG).

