Both treatment arms to complete all visits.	SCREENING	BASELINE (within 28 days of screening)	WEEK 4 (+/- 7 days)	WEEK 12 (+/- 7 days)	WEEK 24 (+/- 7 days)	WEEK 48 (+/- 7 days)	WEEK 52 (+/- 7 days)	WEEK 60 ¹ (+/- 7 Days)	WEEK 72 (+/- 7 days)	WEEK 96 (+/- 7 days)	30 Day FU (+/- 7 days) (by phone)	Early termination visit

 • HsCRP (optional if agreed with sponsor in writing) • Total protein • Sodium • ALT • Albumin • Creatinine clearance (Calculations: Cockcroft-Gault (requires weight), MDRD, CK-Epi) (* including urinary chemistry)												
Fasting Lipids (Fasted for at least 10 hours except at screening) Including: 
 • Total cholesterol • HDL cholesterol • LDL cholesterol • Triglycerides 	X	X	X	X	X	X	X	X	X	X		X
HIV RNA viral load (In event of viral load failure follow section 6.18 for viral failure, resistance assessment & pharmacokinetic assessment procedures)	X	X	X	X	X	X	X	X	X	X		X
Pre-dose Pharmacokinetic assessment (A post-dose sample will be taken at early termination visit and/or in the event of virological failure (see section 6.18) within 20-28 hours of last dose)			X (Experimental arm only)			X (Experimental arm only)	X (Deferred arm only)			X (Both arms)		X
Blood sampling for PBMC isolation (Required unless exemption documented in site contract i.e. if site does not have capacity to process PBMC samples)		X				X				X		X
Quality of Life Questionnaire		X			X	X				X		X

CONFIDENTIAL

	SCREENING	BASELINE (within 28 days of screening)	WEEK 4 (+/- 7 days)	WEEK 12 (+/- 7 days)	WEEK 24 (+/- 7 days)	WEEK 48 (+/- 7 days)	WEEK 52 (+/- 7 days)	WEEK 60 ¹ (+/- 7 Days)	WEEK 72 (+/- 7 days)	WEEK 96 (+/- 7 days)	30 Day FU (+/- 7 days) (by phone)	Early termination visit
Both treatment arms to complete all visits.												
Patient Treatment Satisfaction Questionnaire		X			X	X				X		X
Pittsburgh Sleep Questionnaire		X			X	X				X		X
DDI Assessment		X			X	X				X		X
Adherence Assessment (Self report at visit) (including date and time of last dose on PK days. Including ETV visit and/or in the event of virological failure)		X	X	X	X	X	X	X	X	X		X
AE Assessment		X	X	X	X	X	X	X	X	X	X	X
Con Med Check	X	X	X	X	X	X	X	X	X	X		X
Drug Dispensing (As per pharmacy manual)		X (Experimental arm only)	X (Experimen tal arm only)	X (Experimen tal arm only)	X (Experimen tal arm only)	X	X	X	X			

CONFIDENTIAL

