3.1 Study Objectives

The primary objective of this trial is to compare viral load outcomes on DTG/RPV FDC regimen (experimental arm) to continued ART regimen (control arm) at 48 weeks as measured by HIV-1 RNA below or confirmed ≥ 50 copies/mL.

Secondary objectives are:

- (a) To investigate whether switching patients to DTG/RPV FDC is associated with improvement of lipid profile, patient satisfaction, quality of life and potential for drug-drug interactions, investigated over time through 96 weeks with evaluation (and comparison to control arm) at week 24, 48 and 96.
- (b) To evaluate DTG and RPV trough concentrations
- (c) Changes in cell associated virus (using Peripheral Blood Monoclonal Cell (PBMC) analysis)

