3.2.2 Secondary endpoints/outcomes

Secondary endpoints will include secondary efficacy endpoints, secondary safety endpoints, pharmacological endpoints, and secondary endpoints regarding patient related outcomes.

Secondary efficacy endpoints:

- (a) Proportion of participants with virological failure (2 consecutive viral loads > 50 copies at least 2 weeks apart or a viral load > 50 copies/mL followed by a discontinuation of the study or the study treatment), investigated over 96 weeks.
- (b) Incidence of genotypic resistance in case of confirmed HIV RNA > 50 copies/mL and baseline factors associated with failure i.e. treatment emergent mutations (NRTI, NNRTI, PI and II regions) as compared with previous resistance tests.
- (c) Proportion of participants with plasma HIV-1 RNA < 50 c/mL at week 24, 48 and 96.
- (d) Proportion of participants with virological suppression (< 200 copies/ml HIV RNA) at week 24, 48, 96
- (e) Changes from baseline in cell associated virus using PBMC Illumina MiSeq sequencing at week 48 and week 96.
- (f) Changes from baseline in CD4, CD8 and CD4/CD8 ratio over 96 weeks with evaluation at week 24, 48 & 96.

Secondary safety endpoints:

- (g) Number and percentage of participants with adverse events (AEs), severity of AEs, and treatment discontinuations due to AEs.
- (h) Changes from baseline in laboratory parameter at week 24, 48 and 96.
- (i) Changes from baseline in renal markers, bone markers, and fasting lipids at week 24, 48 and 96.

Secondary endpoints regarding pharmacological outcomes:

- (j) Pre-dose plasma concentrations of DTG and RPV at week 4 (experimental arm only), 48 (experimental arm only) & 96. Plus pre/post-dose (as appropriate) at early termination visit and /or in the event of virological failure a post dose sample will be taken within 20-28 hours.

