10. Pharmacokinetics

[figure not shown]
(j) Pharmacokinetic assessment

Pre-dose plasma concentrations of DTG and RPV at week 4 (experimental arm only), 48 (experimental arm only) and 96. Plus pre/post-dose (as appropriate) at early termination visit and /or in the event of virological failure a post dose sample will be taken within 20-28 hours.

At each time point, the AUC of DTG and RPV post administration will be summarized by the median, Q1, Q3, min, max and number of non-missing values. For each drug, we will compare the evolution of AUC over time using Wilcoxon paired test.

We will use the trapezoidal approach to calculate the area under the curve (AUC). For example, given data t_0, t_1, \dots, t_N and y_0, y_1, \dots, y_N , the area under the curve can be approximated as follows:

$$\int_a^b f(x) dx \approx \frac{1}{2} \sum_{i=1}^N (t_i - t_{i-1})(y_i + y_{i-1})$$
 where t_i is the time value and y_i is the concentration of the antiretroviral drug.

(k) Number of potential DDIs avoided assessment

The number of potential DDIs avoided will be calculated by the difference between the number of interaction drugs graded “amber or red” before and after switching to dolutegravir and rilpivirine. More details are shown in section 3.2.2. The number of DDI avoided will be compared between the two-treatment groups using Mann-Whitney Wilcoxon test. Data will be summarized by the median, Q1, Q3, min, max and number of non-missing values.

11. Other analyses

(l) Changes in quality of life from baseline to week 24, 48 and 96.

The EQ-5D-3L quality of life questionnaires will be analysed using multiple imputation approach to replace missing values (assumption: Missing At Random). Multiple imputation using Chained Equations approach (MICE) will be used to fill in missing data. Therefore, we will create 10 datasets, in which missing data will be imputed from each patient’s other covariables, including all items in the questionnaires, to obtain valid inference and reduce sampling variability resulting from the imputation process. The analysis will include all participants from the mITT population that will complete at least one of the 4 questionnaires (baseline, weeks, 24, 48, and 96). Participants with more than 20% missing data in a specific questionnaire will be excluded from the analysis of the questionnaire.

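### SAP 10(j) plans an AUC and a paired test on it that single pre-dose samples cannot supply, and it leaves out the deferred arm's week-52 sample

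*SAP*

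**What the plan says.** Both documents set the same PK objective: "To evaluate DTG & RPV trough concentrations" in Protocol 2.2 and "To evaluate DTG and RPV trough concentrations" in SAP 3.1. The endpoint in SAP 3.2.2(j) matches it: "Pre-dose plasma concentrations of DTG and RPV at week 4 (experimental arm only), 48 (experimental arm only) & 96". Protocol 2.3.2 and the synopsis list the same weeks.

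The sampling schedule is pre-dose. Protocol 6.8 asks for "Pre-dose blood sampling for measurement of DTG & RPV (PK assessment) (week 4 & 48 (experimental arm), week 52 (deferred switch patients"; a week-96 sample is also taken in each arm. The Appendix 1 table confirms the week-52 sample with the entry "X (Deferred arm only". The PK rows of Appendix 1 and of the SAP schedule both limit the 20-28 hour post-dose sample to early termination or virological failure.

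SAP 10(j) repeats the pre-dose list and then turns to a different quantity: "At each time point, the AUC of DTG and RPV post administration will be summarized by the median". The method is given as follows: "We will use the trapezoidal approach to calculate the area under the curve (AUC". The only test in the section is on that same derived quantity: "For each drug, we will compare the evolution of AUC over time using Wilcoxon paired test". It states no analysis of the pre-dose concentrations themselves. SAP section 7 gives a general descriptive summary for all continuous variables. SAP 6.2 has visit windows for weeks 12, 24, 48, 72 and 96 only.

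**The concern.** The planned analysis does not match the objective, the endpoint or the data. An AUC after dosing describes exposure over an interval and needs serial timed samples. The trial takes a single sample before the dose. The only PK-specific summary and the only PK test in the SAP therefore cannot be produced at scheduled visits, and whoever programs the analysis (SAP section 13 assigns it to Stata) would have to choose a substitute with the data in hand.

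Two gaps go with this. The deferred arm's week-52 sample is collected but no analysis names it, which leaves that arm with week 96 alone and nothing to pair. The SAP also does not say how PK samples are assigned to visits. If the SAP 6.2 windows were used, week-4 samples would have no window, and deferred-arm week-52 samples would be labelled week 48, a time point that the endpoint limits to the experimental arm.

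**Working it through.** The documents give no sample size or power for PK, so there is no stated figure to reproduce. The check compares what 10(j) needs with what the schedule supplies.

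**Can the AUC be computed?**
- The SAP formula is ½ Σ (tᵢ − tᵢ₋₁)(yᵢ + yᵢ₋₁), summed from i = 1 to N over samples indexed 0 to N.
- One sample per visit means N = 0. Trapezoids = samples − 1 = 1 − 1 = 0.
- Coded literally, the formula returns 0 for concentrations of 0.1, 1.0 and 5.0 (arbitrary units). A paired Wilcoxon test on such values returns no p-value.

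**How many samples are affected?** (100 and 50 participants, Protocol 9.1)
- Experimental arm, weeks 4, 48 and 96: 100 × 3 = 300.
- Deferred arm, weeks 52 and 96: at most 50 × 2 = 100.
- Total: up to 400 per drug, giving 0 AUCs.

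**Which within-participant pairs exist?**
- Experimental arm: 4-48, 4-96 and 48-96, so 3 visit pairs.
- Deferred arm as the SAP lists it: week 96 only, so 0.
- Deferred arm with week 52: 52-96, so 1. The total would be 3 + 1 = 4 visit pairs per drug.

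**How many deferred participants could contribute a 52-96 pair?**
- Only control participants with virological success switch at week 48 (SAP 4.1).
- Assumption: the 95% expected success rate (Protocol 9.1) stands in for virological success. Then 50 × 0.95 = 47.5 switch.
- Protocol 6.12 expects 15% loss to follow-up but gives no time frame. If all of it falls after the switch, or is independent of success, 47.5 × 0.85 = 40.4. If loss is constant over 96 weeks and the pre-switch part already sits within the 5% non-success, 47.5 × √0.85 = 43.8. With no later loss the figure is 47.5.
- At 100% success with 15% loss: 50 × 0.85 = 42.5. The ceiling is 50.

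**Where would the PK visits fall in the SAP 6.2 windows?** (visits are ±7 days)
- Week 4: 4 × 7 = day 28, range 21-35. The first window opens on day 43, so the whole range is outside.
- Week 52: 52 × 7 = day 364, range 357-371. The week-48 window is days 295-378, so the whole range is inside it.

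**A separate slip.** SAP 3.2.2(n) and 11(n) list week 72 for the Pittsburgh sleep questionnaire. Protocol 6.8 and Appendix 1 schedule none then, and 11(n) counts four questionnaires while listing five time points.

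**The case against.** The strongest reply is that little is lost. The objective is only to evaluate troughs, and SAP section 7 already fixes a full descriptive summary for them. No objective asks for a comparison over time, and the endpoint is secondary. This stands as a limit on the size of the problem. It does not rescue 10(j), whose summary and test remain impossible as written.

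Other readings of the AUC do not help. An area across study weeks does not fit a value computed at each time point after administration. Treating the trough as constant over 24 hours would make the AUC 24 × trough, but the SAP states no such rule.

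Endpoint (j) also covers failure samples, and SAP 8.2.1(b) lists drug concentration at failure for participants with resistance mutations. That is correct, but the listing does not reach the scheduled troughs.

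The window point is conditional. The SAP applies 6.2 to efficacy outcomes and section 10 does not invoke it, so the need is for a clarifying sentence.

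The pair count also deserves caution. Missing data and discontinuation already count as non-success, so multiplying 0.95 by 0.85 may count some loss twice; hence the range above. The amendment history says week 52 was added to mirror week 4 in the other arm, not to form a pair with week 96. That sample still needs a place in the endpoint and the analysis.

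Finally, the Laboratory Manual is not available, a figure at the head of section 10 is not shown, and the SAP schedule table is damaged. The Protocol's own schedule is nevertheless explicit that sampling is pre-dose.

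**Conclusion.** The concern holds. On the schedules in the documents, 0 AUCs can be computed from up to 400 scheduled samples per drug, so the planned paired test cannot be run. The trough endpoint has a general descriptive summary and no specified comparison. The deferred arm has 0 usable pairs as the SAP stands. Including week 52 would give roughly 40 to 47, at most 50, on the stated assumptions about success and timing of loss; the conclusion does not depend on that figure. The effect is confined to a secondary PK endpoint and should be corrected before the PK analysis is programmed. The visit-assignment gap matters only if the SAP 6.2 windows are applied to PK. The week-72 sleep questionnaire entry is a minor, separate correction.

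**What to change.** - In SAP 10(j), delete the AUC and the trapezoidal formula. Summarise pre-dose DTG and RPV concentrations (median, Q1, Q3, minimum, maximum, n) at weeks 4, 48 and 96 in the experimental arm and weeks 52 and 96 in the deferred arm.
- Apply the planned paired Wilcoxon test to pre-dose concentration within arm, and name in advance which of the four possible visit pairs per drug will be tested.
- Assign PK samples by nominal visit, or add week-4 and week-52 windows.
- Report early-termination and failure samples separately, with actual time since the last dose.
- State how concentrations below the limit of quantification are handled; the SAP's only such rule is for HIV DNA (8.2.1(e)).
- Add week 52 (deferred arm) to the PK endpoint in the Protocol synopsis, Protocol 2.3.2 and SAP 3.2.2(j), and to the SAP schedule if the intact table also omits it.
- Separately, remove week 72 from the sleep questionnaire endpoint and model in SAP 3.2.2(n) and 11(n).

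The cost is wording in the SAP and one endpoint line in two places in the Protocol. No new samples or visits are needed.
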